condition). PD-DLD children will be assigned to one of four conditions of Experiment 1 (n=3 per condition) or one of two conditions of Experiment 2 (n=3 per condition). Following treatment condition assignment, specific treatment target verb stimuli will be identified for each child.

The next set of procedures involve the following, with 1-hour sessions occurring three times weekly (see also C.2.2. *Experimental design*):

- Baseline testing phase, to include administration of the Generalization Probe (a minimum of three baseline sessions per child);
- Treatment phase (maximum 18 sessions), to include
 - Treatment Probe administered at the start of each session and
 - Generalization Probe collected after 9 treatment sessions;
- Post-treatment testing phase, to include Generalization Probe collected immediately following treatment, and at 2 weeks and 2 months posttreatment.

Following completion of the post-treatment testing, children will be dismissed from participation in the research program. Referrals, if needed, for further speech/language services will be provided.

The risks of the procedures associated with the proposed project are minimal and typical of children receiving speech/language services in the schools, with the exception that there is more testing involved, treatment occurs more frequently (three times per week as compared to 1 to 2 times per week in a typical school setting), and the procedures will occur at the university clinic. No individual testing or treatment session will last longer than 1 hour. Risks to the children may include boredom or fatigue. The children will also be informed that they can take breaks or permanently end any session.

Additionally, the frequent visits to the university for participation in the study may incur costs to participants' caregivers in terms of their time and transportation. For that reason, we will offer incentives for participation in the study.

2. Adequacy of Protection Against Risk

a. Informed Consent and Assent: To ensure voluntary participation, the caregivers of potential participants will be asked to return the consent forms in envelopes provided with the informational packet. The consent form will be written in culturally appropriate language that is straightforward and easy to understand. Copies of the signed consent forms will be returned to the caregivers with a reminder of how to contact the research program if they have any questions or concerns. Child assent will be obtained verbally before each session begins.

b. Protections Against Risk: Confidentiality will be maintained by assigning random subject identification numbers when consent forms are returned. This number will be used for all data analyses, testing information, and record keeping. The signed consent forms and list of names linked to the codes will be stored in a locked file cabinet only available to the principal investigators. The written and recorded data will be stored in a separate locked cabinet, available only to the research personnel directly involved in this study. Backups of the digital data will be stored on a password-protected server in the College of Health and Human Services at SDSU.

The risks of the proposed project to the children are minimal and do not exceed those that occur in everyday school life. Fatigue will be minimized by limiting the individual sessions to 1 hour and providing breaks as needed. Costs associated with time and travel will be offset by incentives provided to participants' caregivers.

c. Vulnerable Subjects: Because the purpose of the proposed study is to evaluate treatment target selection for children with PD and/or DLD, all participants will be children, ages 4 to 6 years. This age represents a key time in language development and diagnosis of PD and DLD. The PI ([name]) has conducted various treatment studies for children with PD. The Co-PI ([name]) is a clinically certified speech-language pathologist, specializing in enhancing clinical assessment, particularly for children with DLD. As such, the PI, Co-PI, and the research team have extensive experience conducting standardized and non-standardized language testing of children in this age range. In addition, all personnel working on this project have completed the CITI training program in the protection of human subjects.

3. Potential Benefits of the Proposed Research to Human Subjects and Others

Potential benefits to participating children include speech, language, and hearing screening and treatment, as well as incentive payments given to caregivers as compensation for their time and transportation. The student research assistants will also gain valuable clinical and research skills through their involvement with this project.

4. Importance of the Knowledge to be Gained

The high-incidence disorders PD, DLD, and PD-DLD directly impact a child's ability to communicate and are among the most prevalent developmental disorders. The experiments proposed manipulate the complexity of treatment targets to identify the most efficacious treatment approaches for children who present with these disorders. Our proposal would reveal the nature of interactions between sound and structure in language for these children and will serve as the basis for future treatment studies that will allow children to benefit from treatment in less time than what has been shown to date.

DATA AND SAFETY MONITORING PLAN

The Data and Safety Monitoring Plan (DSMP) below will align with the policies and guidelines of the San Diego State University Human Research Protection Program, from which approval will be obtained prior to any recruitment of study participants begins.

Confidentiality

The study data will consist of digital recordings of children's speech, electronic transcripts of their utterances, and paper records (from study tests). All data will be viewed only by investigators and research assistants and will be entered into a database under password protection. All physical data files will be stored in protected locations and under lock and key except when being viewed by a member of the research team, and will not leave the Phonological Typologies and Child Language Development, Disorders and Disparities Labs. Four-digit participant IDs will replace individuals' names for all purposes, and therefore subject confidentiality will be maintained. Participants will never be identified by name in any publication or report.

Fidelity and Reliability

Periodic fidelity checks will be implemented by the PI, Co-PI, clinical research associate, or senior graduate research assistant to ensure that treatment protocols are administered consistently across participants. For the first 3 participants who enroll in each experiment, weekly checks will occur to verify that procedures and activities are uniform across sessions, and that all participants are given the opportunity to attempt approximately 96 productions per session. These checks will be based on observation of live sessions, review of recorded sessions, and data records. Fidelity checks with subsequent participants will occur during the first treatment week and then every 2 weeks in the same manner. For reliability, 20% of all pretreatment, baseline, treatment, and generalization data from each child will be re-transcribed and re-coded by a second judge (research assistant) trained in SALT,⁴ Phon,³ and IPA notation. Samples with reliability scores <85% will be re-transcribed and/or re-coded completely.

Data and Safety Monitoring Board

The Data and Safety Monitoring Board (DSMB) will consist of independent researchers at San Diego State University who conduct research with human subjects, including vulnerable populations (i.e., children, individuals with neurological impairment, the elderly), and who also engage in clinical research with individuals with communication disorders. They will monitor and evaluate study activities on a quarterly basis to ensure that the DSMP is being followed to the letter. This will entail observing clinical sessions with the study participants, inspection of the research facilities to ensure proper storage of confidential information, and verifying that fidelity and reliability checks are occurring as described above.

The procedures that will be used with the study participants are standard procedures used in current clinical practice. As they are behavioral in nature, they constitute low-risk trials. Further, the PI and Co-PI will not be blinded to the participants' assignments to study conditions, and therefore will be able to monitor all human subject interactions on a weekly, ongoing basis to ensure that the DSMP is being followed. Updates on this monitoring will be reported to the DMSB on a monthly basis.

Should any Adverse Events (AEs) or Unanticipated Problems (UPs) arise, they will be reported to the university Human Research Protection Program, following the guidelines delineated below. In addition, the PI will also report any such AE or UP to the NIDCD, the NIH Office of Biotechnology Activities and the Food and Drug Administration.

Stopping Rules

The study will be discontinued prior to completion in the event that the intervention procedures are directly associated with AEs, suggesting that the intervention is unsafe.

San Diego State University Adverse Event Reporting

The SDSU Human Research Protection Program's guidelines for reporting AEs and UPs are as follows
[http://research.sdsu.edu/research_affairs/human_subjects/guidance]

- A. Adverse Event and Unanticipated Problems Reporting
 1. Reportable Events/Problems
 - a. All unanticipated problems involving risk
 - b. Unanticipated Serious Adverse Events

Serious adverse events must be reported to the IRB immediately at least within 48 hours of the event. Serious adverse events are defined as (i) events that have resulted in death; (ii) are life threatening; (iii) require inpatient hospitalization; (iv) result in persistent or significant disability/incapacity, (v) result in a congenital anomaly/birth defect; or (vi) any other adverse event that, based upon appropriate medical judgment, may jeopardize the subject's health and may require medical or surgical intervention to prevent one of the other outcomes listed in this definition (examples of such events include allergic bronchospasm requiring intensive treatment in the emergency room or at home, blood dyscrasias or convulsions that do not result in inpatient hospitalization, or the development of drug dependency or drug abuse). All other problems (listed below) must be reported to the SDSU IRB within 5 days.

- c. Any apparent serious and/or continuing non-compliance.
- d. Protocol deviations
- e. Any unauthorized use, disclosure, removal, theft, or loss of PHI or individually identifiable private information.

Examples of losses under item (e) above include but may not be limited to:

- a. Signed consent forms, data collection forms or case report forms containing PHI
- b. The loss or theft of a laptop, flash drive, smart phone or tablet containing private identifiable information.

B. How to Submit a Report of a Problem in Research

Please access the Adverse Event Report form on the HRPP website at:

https://newscenter.sdsu.edu/researchaffairs/files/03111-SDSU_HRPP_Adverse_Event_Form.pdf and submit the form as an email attachment to [contact]. For more information contact the HRPP office at [contact].

C. Review of a Report of a Problem in Research

The IRB will review the report to determine if the adverse event or problem is serious, unanticipated and related to the research. The IRB Chairperson will also determine if immediate action is warranted.

D. Convened IRB Review of a Report

When the IRB Chairperson determines the event is serious, unanticipated and related, the report will be reviewed at next IRB meeting. The Senior Research Affairs [IRB] Analyst will assign a primary reviewer to review and present the event at the meeting. The primary reviewer as well as all IRB members have access to the vIRB and are expected to review the report in prior to the meeting.

The IRB will consider the following actions:

1. Modification to the protocol
2. Modification of information in provided in the informed consent document and during participant consenting
3. Providing additional information to past study participants
4. Notification of current study participants if the new information might affect their willingness to continue participation
5. Requiring the re-consent of currently enrolled participants
6. Modification to the continuing review schedule
7. Monitoring of the research
8. Monitoring of the consent process
9. Suspension of research
10. Termination of research

E. For Cause Suspension or Termination of IRB Approval of Research

The IRB Chairperson or designee may require an immediate, temporary suspension of enrollment of new participants and/or continued participation of previously enrolled participants, pending convened IRB review of an adverse event, unanticipated problem involving risk or research that is not being conducted in accordance with IRB requirements.

Upon review, if the IRB determines there is an unanticipated problem involving risk, or that there is serious continuing non-compliance, they may vote to suspend or terminate approval of the research.

The IRB will notify the PI in writing of such suspensions or terminations. The correspondence will include a statement for the reasons for suspension or termination. The PI will be provided with an opportunity to respond to the IRB in person or in writing.

F. Mandatory Reporting to SDSU Institutional Officials and External Agencies

Reports of any suspension or termination of IRB approval will be promptly reported to the appropriate institutional officials, the HHS agency that supports the research, and OHRP. The reports will include the reasons for the IRB's action as well as:

1. The name of the institution(s) (e.g., university, hospital, foundation, school, etc.) conducting the research project;
2. The title of the research project and the title of any related grant, contract, or cooperative agreement;
3. The name of the principal investigator for the research project;
4. The number of the research project assigned by the IRB and the number of the applicable HHS award(s) (grant, contract, or cooperative agreement);
5. A detailed description of the reason for the suspension or termination; and
6. The actions the institution is taking or plans to take to address the suspension or termination (e.g., investigate alleged noncompliance, educate the investigator, educate all research staff, require monitoring of the investigator or the research project, etc.)

When an IRB (a) suspends or terminates its approval during the period for which IRB approval had already been given or (b) disapproves a research project at the time of continuing review, the IRB should establish procedures to ensure that the rights and welfare of currently enrolled subjects are protected, subjects are not put at risk, and subjects receive appropriate care, if indicated, during the period of suspension or following the cessation of the research. This is particularly important in the context of clinical trials. For example, the IRB, in consultation with the investigator and the subjects' treating physicians (if not the investigator), may need to determine whether it is in the best interests of currently enrolled subjects to (a) continue receiving the interventions that were being administered to subjects under the research project, (b) be transferred to another institution engaged in the research so that participation of the subjects in the research may continue, or (c) be transitioned to medical management outside of the research context. Continuation of subjects on interventions that were being administered under the research project may be appropriate at least temporarily, for example, when those interventions hold out the prospect of direct benefit to the subjects or when withholding those interventions poses increased risk to the subjects. If the IRB decides that already enrolled subjects should continue to receive the interventions that were being administered to subjects under the research project, data collection (especially safety information) should also continue for such subjects.

In the case of an adverse event or other research related problem, the IRB will determine whether the investigator has developed appropriate measures to remedy the problem and to avoid the occurrence of a similar problem in the future. If the IRB determines that the adverse event [or other problem] is related to the research and that the problem was unanticipated, the PI will be asked at a minimum to modify informed consent procedures so that current participants are notified of the event so that they may determine whether or not they wish to continue their participation. The investigator may also be required to revise the informed consent process for use with future participants so that all foreseeable risks that are involved in the study are described. In addition, the IRB will determine on a case-by-case basis whether additional substantive changes such as major revisions to the protocol are required.

Federal law may also require the IRB to report the incident to the Office of Human Research Protections (OHRP) (45 CFR 46.103(a)). The IRB will report the incident to OHRP when it has been determined that the adverse event is also considered an unanticipated problem and therefore meets all of the following criteria:

1. The adverse event is unexpected in nature, severity and frequency;
2. The adverse event is related or possibly related to participation in the research; and
3. The adverse event suggests that the research places subjects or others at greater risk of physical or psychological harm than was previously known or recognized.

(Modified from OHRP's "Algorithm for Determining Whether an Adverse Event is an Unanticipated Problem" available: <http://www.hhs.gov/ohrp/policy/AdvEvntGuid.htm>, p. 10).

Adverse events that do not meet the criteria as described above will not be reported to OHRP; however the SDSU IRB maintains that authority to require protocol revisions or suspend or terminate any protocol that is not being conducted in accordance with the SDSU IRB requirements for approved research or that has been associated with unexpected serious harm to subjects. The IRB will promptly notify the investigator if this determination is made.

G. Recognizing a Deviation from an IRB Approved Protocol

The IRB presumes the PI is implementing protocol procedures consistent with IRB approval. However, the IRB recognizes that deviations and exceptions to approved IRB protocols may occur. A protocol deviation occurs when there is inconsistency between the procedures carried out in a study and the procedures stated in the research protocol, or when regulations regarding the manner in which research is being conducted are not being followed. Protocol deviations may directly harm or present the risk of harm to human subjects, or may be administrative in nature, such as those related to data or record keeping. As indicated in section XI, protocol deviations should be reported to the IRB.

STATISTICAL DESIGN AND POWER

This study employs a single-subject, staggered, multiple-baseline design.^{82,117-119} Consistent with this design, it includes a standard (minimum) number of subjects per study condition (n=3). Experiment 1 includes four different treatment conditions and two populations, and thus includes 24 participants (3 participants x 4 conditions x 2 populations). Experiment 2 includes two different treatment conditions and two populations, and thus includes 12 participants (3 participants x 2 conditions x 2 populations).

Consistent with the staggered MBL design, analyses will focus on individual performance. We will complete a visual inspection of accuracy data plotted over time for each child.^{116,118,132} Level, slope, and variability of accuracy scores across all data points will be evaluated within and across children to compare different legs of the multiple baseline within and across treatment conditions for each experiment.^{118,119,133} This type of individual case data allows us to examine individual differences in performance during and following treatment and is particularly meaningful to practicing speech-language pathologists.

In addition, clinically meaningful effect size will be determined by calculating the difference in mean accuracy across pretreatment probes and mean accuracy posttreatment divided by the standard deviation of accuracy post-treatment on the Generalization Probe.^{73,116} Effect sizes obtained for each treatment condition in each experiment will be compared relative to one another, and to results from published studies reporting effect size.

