4.3. Outcome Measures

Name	Treatment Probe	
Type	Primary	
Time Frame	All participants will complete the Treatment Probe at the start of each treatment session. Maximum 18 sessions.	
Description	The Treatment Probe is made of the selected treatment stimuli (verbs) that are consistent with the child's assigned experimental condition. These verbs have a final consonant or consonant clusters ("sees" vs. "seats"), and are mono- or bi-morphemic ("tease" vs. "sees"). Children will be asked to pronounce each word following presentation of a corresponding picture and a verbal prompt. The Treatment Probe allows us to track the effectiveness of treatment on the treated stimuli.	
Name	Generalization Probe	
Type	Primary	

Time Frame	All participants will complete the Generalization Probe during baseline phase (minimum 3 times), after 9 treatment sessions, after the last treatment session, and 2 weeks post-treatment.
Description	The Generalization Probe consists of words and phrases that target each consonant, cluster, and morpho-syntactic constructs a minimum of 10 times across relevant contexts (i.e., word- and utterance-position). The Generalization Probe allows us to track the effects of treatment (generalization) to untreated stimuli and to monitor control variables.

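### Conditions are compared on a gain divided by a post-treatment SD that rests on 2 or 3 probes per child, so the condition with the smaller gain can come out first

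*Combined protocol and SAP*

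**What the plan says.** Statistical Design and Power opens with visual inspection of each child's accuracy plotted over time, judging level, slope and variability within and across children and conditions. It then adds one numerical summary, the difference between mean accuracy over the baseline probes and "mean accuracy posttreatment divided by the standard deviation of accuracy post-treatment on the Generalization Probe". On its use it says: "Effect sizes obtained for each treatment condition in each experiment will be compared relative to one another". The results are also to be set against published effect sizes.

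The level of computation is not given. "analyses will focus on individual performance" points to one effect size per child; the phrase about effect sizes for each condition points the other way. The text supplied has no rule for an SD of zero and names no numerical summary of raw gain.

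The number of post-treatment probes differs between sections. Section 4.3 (Outcome Measures) schedules the Generalization Probe "after the last treatment session, and 2 weeks post-treatment", which makes two. Study Procedures, under Protection of Human Subjects, has it "collected immediately following treatment, and at 2 weeks and 2 months posttreatment", which makes three. Both ask for at least three baseline probes. Each condition has three children per population.

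**The concern.** An SD from two or three values is a very unstable divisor, and here each child or condition has its own. Two children with the same true variability and the same gain can get very different effect sizes, and a child whose post-treatment scores happen to agree gets a huge or undefined one.

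There is also a systematic problem. The post-treatment probes are taken weeks apart. A child who keeps improving, or loses ground, after treatment has a larger SD for that reason, and so a smaller effect size for the same mean gain. Continued improvement on a generalization measure would be penalised.

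The study exists to compare treatment conditions, and this is the only numerical summary defined for doing so. A published effect size could therefore favour the condition whose children improved less.

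**Working it through.** **Inputs from the documents.** Three children per condition and population; at least 3 baseline probes; 2 or 3 post-treatment probes; at least 10 items per target (section 4.3). The plan gives no effect size, SD or power to reproduce. Its sample sizes are counts, and they check: 3 × 4 × 2 = 24 and 3 × 2 × 2 = 12, total 36.

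**Assumed.** Gains, SDs, accuracy levels and the number of items in a score. The documents give none of these.

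**1. Stability of the SD.** For k normal scores, s/σ = √(χ²(k−1)/(k−1)). Its 95% range is 0.03 to 2.24 for k = 2 and 0.16 to 1.92 for k = 3. Two children with the same true SD have sample SDs at least 2-fold apart with probability 0.59 (k = 2) or 0.40 (k = 3).

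**2. Reversal by example** (baseline 10%, 10-item scores; d = gain / SD).

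| Post-treatment scores | Gain | SD | d |
|---|---|---|---|
| 60, 90 | 65 | 21.2 | 3.1 |
| 30, 40 | 25 | 7.1 | 3.5 |
| 60, 80, 90 | 66.7 | 15.3 | 4.4 |
| 30, 40, 40 | 26.7 | 5.8 | 4.6 |

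In each pair the smaller gain has the larger d.

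**3. How often conditions are misordered.** Simulation with true gains 40 v 20, 3 children per condition, 3 baseline probes and normal scores with within-child SD 10. Per child: d for each child, averaged over three. Per condition: mean gain over one SD from all 6 or 9 post-treatment scores. Entries are the share of comparisons in which the poorer condition ranks first, for 2 / 3 post-treatment probes. Where a trend is present, scores change by 20 points in total around the same mean.

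| Scenario | d per child | d per condition | Raw gain |
|---|---|---|---|
| No trend, no between-child SD | 27% / 15% | 10% / 6% | 0.4% / 0.1% |
| Between-child SD 10 | 27% / 17% | 14% / 11% | 3.5% / 2.9% |
| Between-child SD 20 | 29% / 22% | 22% / 20% | 13% / 13% |
| Trend in better condition only | 52% / 32% | 29% / 17% | under 1% |
| Trend in both | 24% / 13% | 8% / 5% | under 1% |
| Trend in poorer condition only | 10% / 5% | about 2% / 1% | under 1% |

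The trend rows have no between-child SD. With binomial scores (baseline 10%, post-treatment 50% v 30%, 10 to 50 items, tied children left out) the rates are 15–19% / 12–15% per child, 11–14% / 6–9% per condition and 0–2% on raw gain.

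A third reading takes the SD across the three children's scores. With equal between-child SDs of 10 to 20, it misorders 21–24% of comparisons against 1–11% for raw gain.

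**4. Spread for one child.** With gain 40 and SD 10 (true value 4), the central 90% of d runs from 1.8 to 64 with 2 probes and from 2.1 to 18 with 3.

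**5. Undefined values.** P(SD = 0) is the sum of squared (2 probes) or cubed (3 probes) binomial probabilities.

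| True accuracy | 10 items | 50 items |
|---|---|---|
| 70% | 19% / 4% | 9% / 1% |
| 90% | 31% / 11% | 13% / 2% |

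With one SD per condition, ties nearly vanish.

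**The case against.** The effect size is an addition. The lead analysis already looks at level, slope and variability within and across conditions, so a 65-point gain would be seen beside a 25-point gain, and no test or threshold rests on d. That stands, and it limits the severity. It does not correct a reported effect size that orders the conditions the other way.

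The size of the problem depends on assumptions. The worst rates need a trend in the better condition only, which nothing in the documents suggests; a trend in both gives rates slightly below the no-trend case. The very low raw-gain rates need little spread between children; at between-child SD 20, raw gain itself misorders 13%. Ties become rare if many targets are combined: with 200 items at 70% accuracy they fall to about 4% / 0.2%. All of this is fair, and the rates should be read as a range. In every scenario examined, d still misordered more often than raw gain.

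The level of computation and a zero-SD convention may be stated in the cited method papers or in the experimental-design section that is referred to but not supplied. That cannot be excluded. It would settle the ambiguity, but not the instability or the effect of post-treatment change.

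A pooled SD has a weakness too. PD and PD-DLD children enter at no more than 20% accuracy on final consonants and clusters, so baseline SDs may be small. If they were 3 at baseline and 10 after treatment (assumed), the pooled SD in Experiment 1 with two post-treatment probes would be √((48 × 9 + 24 × 100)/72) ≈ 6.3, making every effect about 1.6 times larger than with an SD of 10. This affects the scale, not the ordering, and it should be disclosed.

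**Conclusion.** The concern holds. That the statistic can reverse the order of gains follows from its formula and needs no assumption. How often it does so depends on values the plan does not give: with true gains of 40 v 20 and no trend confined to one condition, about 13–29% on the per-child reading and about 5–22% with one SD per condition, always above raw gain under the same assumptions. The effect size comes second to visual inspection, so the fault lies in the numerical comparison of conditions and not in the whole analysis. It should be fixed.

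**What to change.** In Statistical Design and Power:

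- Make the raw percentage-point gain, per child and per condition, the basis for comparing conditions. Show end-of-treatment and follow-up gains separately, so that later change is reported and not absorbed into an SD.
- If a standardised effect is wanted, divide by one common SD per experiment: the within-child, within-phase SD pooled over all children. Being the same for every condition, it keeps the raw-gain order. With exactly 3 baseline probes it has 24 × 2 + 24 × 1 = 72 degrees of freedom in Experiment 1 (24 × 2 + 24 × 2 = 96 with three post-treatment probes) and 12 × 2 + 12 × 1 = 36 in Experiment 2 (48 with three). State that it mixes baseline and post-treatment variability.
- Keep the planned effect size only as a supplement for comparison with published studies. State whether it is computed per child or per condition, and what is done when the SD is zero.
- Reconcile section 4.3 and Study Procedures on the 2-month probe.

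The cost is three or four sentences and no new data. The pooled effect can be compared only with studies that used a similar standardiser; the supplementary statistic keeps the planned comparison possible.

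### Published effect sizes are to serve as a benchmark without being put on the trial's own standardiser, so equal accuracy gains can receive different values

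*Combined protocol and SAP*

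**What the plan says.** All of the relevant analysis text is in the Combined protocol and SAP, under Statistical Design and Power.

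- The main analysis is visual: each child's accuracy is plotted over time and judged on level, slope and variability.
- As an addition, an effect size is obtained by "calculating the difference in mean accuracy across pretreatment probes and mean accuracy posttreatment", "divided by the standard deviation of accuracy post-treatment on the Generalization Probe". The text does not say whether that SD is taken within a child or across children.
- The effect sizes for each condition "will be compared relative to one another, and to results from published studies reporting effect size". That is all the plan says about the external comparison. It names no studies and mentions no recomputation, and it gives no benchmark value and no rule for reading the result.

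Other sections supply the context. Study Procedures plans "a minimum of three baseline sessions per child" and caps treatment at 18 sessions. Section 4.3 describes the Generalization Probe as a primary outcome on untreated material, with at least 10 items per target. Three diagnostic groups are enrolled: PD (12), DLD (6) and PD-DLD (18).

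**The concern.** A standardised effect size has no meaning apart from its denominator. The plan divides by the post-treatment SD. A published value may divide by a baseline SD or a pooled SD, and it is then on a different scale even where the children improved by exactly the same number of percentage points.

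In this population there is a plausible reason for the two SDs to differ. Children who start near the floor have little room to vary at baseline and more room once accuracy has risen to mid-range.

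At stake is how the external benchmark is read. Conditions in this trial could look weaker or stronger than published results because of the formula alone. Number of sessions and diagnostic group can also differ between this trial and a published study, and the plan does not say that they will be shown.

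**Working it through.** **The plan's own figures.** The section gives no benchmark effect size, SD or threshold, so there is none to reproduce. Its sample size does reproduce (3 × 4 × 2 = 24, plus 3 × 2 × 2 = 12, total 36) and is not affected by this point.

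**Inputs.**
- Formula: gain over post-treatment SD (Statistical Design and Power).
- Items per target: 10, the minimum in section 4.3.
- Starting accuracy p0 of 5%, 10% and 20%: assumed. The 20% figure borrows the eligibility cap in section 2.2. Protection of Human Subjects, 1a, shows that this cap is a PEEP screening criterion. It applies to PD and PD-DLD only (12 + 18 = 30 of 36 children) and is not a Generalization Probe baseline. DLD children must exceed 20%.
- Final accuracy p1: assumed.
- SD: assumed binomial, SD(p) = √[p(1 − p)/10]. The documents give no SD.

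**Formulas.** Effect size = (p1 − p0)/SD, with the SD at post-treatment (the plan), at baseline, or pooled as √[(SD0² + SD1²)/2]. The ratio of the baseline-SD value to the plan's value is √{p1(1 − p1)/[p0(1 − p0)]}. The number of items cancels, so the ratio does not depend on the 10.

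**Results.**

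| Rise | Post-treatment SD (plan) | Pooled SD | Baseline SD | Baseline ÷ plan |
|---|---|---|---|---|
| 20% to 50% | 0.30/0.158 = 1.90 | 2.10 | 0.30/0.126 = 2.37 | 1.25 |
| 10% to 50% | 0.40/0.158 = 2.53 | 3.07 | 0.40/0.095 = 4.22 | 1.67 |
| 5% to 50% | 0.45/0.158 = 2.85 | 3.69 | 0.45/0.069 = 6.53 | 2.29 |
| 20% to 80% | 0.60/0.126 = 4.74 | 4.74 | 0.60/0.126 = 4.74 | 1.00 |
| 20% to 90% | 0.70/0.095 = 7.38 | 6.26 | 0.70/0.126 = 5.53 | 0.75 |

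For rises to 40% or 60%, p1(1 − p1) = 0.24 and the ratio is √(0.24/0.16) = 1.22 from 20%, √(0.24/0.09) = 1.63 from 10% and √(0.24/0.0475) = 2.25 from 5%. Over final values of 40–60% the range is thus 1.22 to 2.29. The pooled-SD value is 1.10 to 1.30 times the plan's over the same range.

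**Reading the direction.** A ratio above 1 means that a published baseline-SD value exceeds the trial's for the same gain, so the trial looks worse. At 0.75 the trial looks better.

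**Without the binomial assumption.** Take a 30-point gain and assumed SDs in percentage points:
- Baseline 5, post 15: the plan gives 30/15 = 2.0, baseline SD gives 30/5 = 6.0, pooled gives 30/√125 = 2.7.
- Both 10: all three give 3.0.
- Baseline 15, post 5: the plan gives 6.0, baseline SD gives 2.0, pooled gives 2.7.

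**Amount of treatment.** A common formula does not remove this difference. If gain were linear in sessions (assumed: 30 points at 18 sessions, SD 10), the effect size would be 15/10 = 1.5 at 9 sessions and 3.0 at 18. This is why session counts should stand beside each comparator.

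**The case against.** The strongest reply is that this is a short descriptive clause at the end of the analysis text. The plan puts visual analysis first, and its comparison between conditions uses one formula throughout. No test, threshold or decision rests on published values. All of that stands, and it confines the point to the external benchmark.

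Several stronger readings are tempting, and the documents do not support them.

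- *The trial will reach a wrong conclusion about existing treatment.* The plan promises no superiority claim. The phrase about helping children "allow children to benefit from treatment in less time than what has been shown to date" describes future studies built on this one. The aim of finding the most efficacious approaches is tied to the complexity of targets, which the trial's own conditions vary.
- *The published comparison is the only control.* Each child has repeated baseline probes. The table of conditions is not in the available text, so whether any condition resembles usual targets cannot be judged.
- *Any published study qualifies.* The clause is not worded as an eligibility rule. The formula carries two citations, and Study Procedures points to a design section that is not in the available text; matching rules could be there.
- *The published values are known to be mismatched, or the bias runs one way.* Their formulas are not in the documents. Rises to 40–60% sit where binomial variance peaks, so they give the largest ratios; larger rises remove or reverse the difference.

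What survives is narrower: the available text allows values on different scales to be set side by side, and nothing in it prevents this.

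**Conclusion.** The point holds as a limited one. The plan compares its post-treatment-SD effect sizes with published effect sizes without requiring a common standardiser. If the published values use a baseline SD, the same gain is valued at 1.22 to 2.29 times the plan's figure for rises from 5–20% to 40–60%, at 1.00 times for 20% to 80%, and at 0.75 times for 20% to 90%. These figures rest on a binomial SD and on assumed starting and final accuracies. With equal SDs before and after treatment the discrepancy disappears, although sessions and diagnostic group may still differ.

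A reader might infer that the trial's efficacy findings are compromised. They are not: the within-child visual analysis and the comparison among the trial's own conditions do not use the published values. This is an inexpensive improvement to a secondary benchmark.

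**What to change.** In Statistical Design and Power, replace the clause on published studies with text such as:

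> Published results will be compared on the effect-size scale only after they have been recomputed with this study's formula on generalization (untreated-item) outcomes. Where that is not possible, only the raw gain in percentage points will be compared. The number of sessions and the diagnostic group (PD, DLD or PD-DLD) will be shown beside each comparator. The comparison is descriptive.

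Recomputation needs a fully stated formula, so the same paragraph should say whether the SD is within or across children and which probes enter it. On the probes, section 4.3 lists "after 9 treatment sessions, after the last treatment session, and 2 weeks post-treatment", while Study Procedures lists "Generalization Probe collected immediately following treatment, and at 2 weeks and 2 months posttreatment". The two must be reconciled, because the 2-month probe can change the post-treatment SD.

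The cost is a paragraph of text and some data extraction from published reports. Fewer published studies will be usable on the effect-size scale. Sample size, visits and measurements to be taken need not change on account of the new clause.
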